1.2 Human Laboratory Studies

Human laboratory studies of acute responses to alcohol, alcohol cues, or other experimental manipulations have progressed in important ways and hold potential to advance our understanding of how medications exert beneficial effects on drinking outcomes (18). These studies may help identify important individual difference factors affecting alcohol response, such as personality traits, drinking characteristics, and genotype, and aid in our understanding of the variability in cue and craving states, and provide additional information relevant to the design of clinical studies to assess the effectiveness of pharmacological agents.

The study to be conducted in this protocol utilizes an alcohol cue reactivity paradigm to attempt to recreate in the human laboratory risk conditions for relapse like those experienced by individuals with AUD in their natural environment. Alcohol cue reactivity, which involves systematic exposure to *in vivo* alcohol cues and simulates high-risk situations for relapse, is one of the most widely studied laboratory paradigms in the context of AUD (19, 20). Exposure to alcohol cues reliably elicits responses presumed to relate to the motivational processes that underlie drinking (21), and it is sensitive to medication effects among treatment seeking and non-treatment seeking adults and adolescents.

Impact on individual variability. Reactivity to alcohol and other drug cues varies from person to person, with some individuals showing little or no increase in target variables (e.g., craving) from the baseline or neutral cue trials to alcohol/drug cue trials (22-25). Some researchers have operationalized "responders" as individuals who show any change (22, 23, 26-28), whereas others have specified an exact minimum change (e.g., > 1-point increase in average craving) (25, 29, 30). Potential sources of variability include sex (31), genetic factors (32, 33), personality (26, 34), and substance use factors, such as lifetime alcohol

use indices and parental drinking problems (35), and these individual differences may moderate the effects of medications on alcohol cue reactivity (36-38).

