1.4 General Investigative Plan

This proof-of-concept study is a double-blind, randomized, placebo-controlled, parallel group, single-site clinical trial. After obtaining consent/parent permission/assent, potential subjects and, if younger than 18 years, their parent(s) will complete a medical history and psychiatric diagnosis interview (about the adolescent) to screen for eligibility. Youth will also complete a physical examination, vital signs, drinking history by the timeline follow-back (TLFB) method, alcohol breathalyzer test, Clinical Institute Withdrawal Assessment for Alcohol-revised (CIWA-AR), prior/current medication use, urine toxicology screen, clinical chemistry, and the Columbia Suicide Severity Rating Scale (CSSR-S). Females of child-bearing potential will have a pregnancy test.

If eligible for the study, 50 subjects will be randomized in an approximate 1:1 ratio (targeting 21 subjects per group – 42 subjects total who complete the protocol) to either atomoxetine or placebo for 6 weeks.

Atomoxetine will be dosed at 40 mg/day for three days then increased to the maintenance dose of 80 mg (active) taken orally once daily (QD) for an additional 5.5 weeks. Subjects randomized to the placebo condition will be given an equal number of visually matched capsules.

As shown in Figure 1, subjects will be seen in the clinic (or remotely) at the screening appointment, the randomization/baseline session, and at weekly visits during the study. At the randomization/baseline visit and after 4 weeks of investigational product administration (i.e., Study Week 5), subjects will undergo a human laboratory paradigm (i.e., alcohol cue reactivity assessment).

[figure not shown]

Figure 1: Overview of Study Chronology

Study Objectives

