4.6 Measures Taken to Minimize/Avoid Bias

4.6.1 Randomization

If eligible for the study, subjects will be randomized in an approximate 1:1 ratio (N = 50; targeting 21 subjects per group – 42 subjects total) to either atomoxetine or placebo for 6 weeks. Urn randomization will ensure approximately equal representation of males and females.

If the subject is randomized and is never dispensed study drug, then the subject will be considered a randomization failure and an additional subject will be randomized with the next randomization sequence at the time s/he is randomized. Likewise, if the subject was randomized and then is determined to not be eligible for the study and never received study drug, then another subject will be randomized such that the total numbers of subjects who were eligible, randomized, and dispensed study drug meet the enrollment goals. In the case of a subject who was eligible, randomized, and dispensed study drug but did not return for follow-up visits, this subject will not be replaced. Any subject who received study drug but was later determined to be ineligible will likewise not be replaced. The reason(s) that a subject was considered a randomization failure or screen failure will be documented in source documents and case report forms (CRFs).

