8.2 Secondary Outcome: Alcohol Craving Assessed in the H-LAB Paradigm

The secondary endpoint will be alcohol craving assessed during a laboratory alcohol-cue exposure paradigm, at study week 5. During the paradigm, participants rated their alcohol craving immediately following exposure to water cues and again immediately following exposure to alcohol cues. The primary outcome measure will be is the number and percentage of participants who report any level of alcohol craving during a laboratory alcohol-cue exposure paradigm (following exposure to alcohol cues) using the following single item: *How strong is your craving to drink alcohol?* Scores range from 0 (None) to 20 (Extremely Strong). Individuals who endorse any level of alcohol craving (e.g., > 1) are considered to

experience craving. Individuals who do not report any alcohol craving (e.g., 0) will be regarded as non-craving. Using generalized estimating equations, we compared the likelihood of alcohol craving as a function of medication condition.

Quality Control and Quality Assurance

This study will be conducted under International Conference on Harmonization (ICH) Good Clinical Practice (GCP) guidelines and all applicable regulatory requirements.

Actions to ensure the accuracy and reliability of data include the selection of qualified investigators and appropriate study centers; the review of protocol procedures with the investigator and study personnel prior to study start; the design of suitable source documents with appropriate instructions for use; the internal audit of source data according to GCP and internal procedures to ensure their accuracy, completeness, and verifiability; as well as the periodic site monitoring by the Sponsor's representatives (clinical monitors). The Project Coordinator or Project Director will review source documents and CRFs for accuracy and completeness. Any discrepancies will be resolved with the investigator, as appropriate.

Audits and Inspections

Authorized representatives of the Sponsor and the IRB may visit the site to perform audits or inspections, including source data verification. The purpose of the audit or inspection is to systematically and independently examine all study related activities and documents to determine whether these activities were conducted, and data were recorded, analyzed, and accurately reported according to the protocol, GCP guidelines, and any applicable regulatory requirements.

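### Sex is the only named urn factor and a possible source of cue-reactivity variation, but the craving comparison in 8.2 does not use it; if sex is prognostic, some power is lost

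*Combined protocol and SAP*

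**What the plan says.** Section 4.6.1 (Randomization) says that "subjects will be randomized in an approximate 1:1 ratio", with "N = 50; targeting 21 subjects per group". Section 1.4 describes the target as "42 subjects total who complete the protocol". The only factor attached to the urn is sex: "Urn randomization will ensure approximately equal representation of males and females". The sentence does not say that the balance is between arms, but under a heading on minimising bias that is the natural reading.

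Section 1.2 (Human Laboratory Studies) states: "Potential sources of variability include sex (31), genetic factors (32, 33), personality (26, 34), and substance use factors". It adds that "these individual differences may moderate the effects of medications on alcohol cue reactivity". It gives no effect size for sex.

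Section 8.2 makes the craving outcome binary (any craving versus none after alcohol cues, at week 5). It specifies generalized estimating equations in which "we compared the likelihood of alcohol craving as a function of medication condition". It names no covariate, link, working correlation or effect scale. Sex does not appear as an analysis variable anywhere in the document.

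**The concern.** The trial constrains its randomisation on one variable, names that variable as a possible source of variation in the paradigm that yields the endpoint, and then does not mention it in the analysis. When arms are balanced on a prognostic factor, the difference in proportions varies less from trial to trial than an unadjusted standard error assumes. The unadjusted test then rejects a true null less often than its nominal level and detects a real effect less often than it could.

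With about 21 per arm there is little power to spare. At two-sided 5%, 80% power needs a contrast of roughly 60% versus 19% craving.

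There are two further reasons to settle the matter in advance. Urn balance is approximate at this size, and section 5.3 keeps anyone who stops study drug before week 5 out of the second laboratory session. Balance on sex among those analysed is therefore not assured. And because 8.2 is silent on covariates, whether to include sex could be decided after the data are seen.

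**Working it through.** **Inputs from the documents.** 50 randomised, about 1:1; 42 targeted as completers (42/50 = 84%, an implied loss of 16%); urn on sex; binary endpoint; GEE with medication as the only named term. The plan states no power, alpha or standard error for this comparison, so there is no figure to reproduce.

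**Assumptions.** Two-sided 5%; 42 analysed, half female; one binary outcome per subject; the same treatment odds ratio in both sexes; treatment log odds ratio 0 (null) or -1.5. Placebo craving rates by sex are assumed and varied.

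**Step 1: analytic, risk-difference scale.** With exact balance on sex, mean craving rate p and male-female gap g, under the null:

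true variance / unadjusted variance = 1 - (g/2)² / [p(1 - p)]

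actual alpha = 2[1 - Φ(1.96 / √ratio)]

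For p = 0.60, p(1 - p) = 0.24. At g = 0.40 the ratio is 1 - 0.04/0.24 = 0.833.

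| Gap (points) | Variance ratio | Unadjusted SE too large by | Actual alpha |
|---|---|---|---|
| 0 | 1.000 | 0% | 5.0% |
| 10 | 0.990 | 0.5% | 4.9% |
| 20 | 0.958 | 2.2% | 4.5% |
| 30 | 0.906 | 5.0% | 4.0% |
| 40 | 0.833 | 9.5% | 3.2% |

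The urn balances less tightly than this. In simulation with urn allocation within sex, the mean unadjusted SE against the true SD under the null was 0.1518 against 0.1510 at a 20-point gap (0.5% too large) and 0.1524 against 0.1422 at 40 points (7%).

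**Step 2: the planned type of model.** Logistic model with robust (GEE sandwich) SE, urn within sex, mean placebo rate 60%, 6,000 trials per setting.

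| Gap (points) | Power without sex | Power with sex | Gain (points) | Type I error without / with sex |
|---|---|---|---|---|
| 0 | 63.3% | 63.9% | 0.6 | 4.6% / 4.8% |
| 10 | 61.1% | 61.8% | 0.7 | 4.1% / 4.4% |
| 20 | 59.5% | 61.5% | 2.0 | 4.7% / 5.2% |
| 30 | 54.5% | 58.1% | 3.6 | 4.2% / 5.0% |
| 40 | 46.7% | 52.8% | 6.1 | 3.3% / 4.4% |

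Monte Carlo error is up to about 0.6 points on each power and 0.3 on each type I error. Fits that did not converge were dropped, at most 162 of 6,000 (2.7%).

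**Step 3: a stratified test.** Pooled z test against Cochran-Mantel-Haenszel stratified by sex, urn within sex, log odds ratio -1.5.

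| Placebo craving by sex | Gap (points) | Power, pooled z | Power, stratified | Unadjusted type I error |
|---|---|---|---|---|
| 80% / 65% | 15 | 62% | 63% | 4.9% |
| 85% / 60% | 25 | 56% | 59% | 4.6% |
| 90% / 50% | 40 | 43% | 52% | 3.8% |

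With no sex effect, stratifying cost nothing material. If the arms were exactly balanced on sex, the 90% / 50% row would be 41% against 53%, a gain of 12 points; the urn does not guarantee that balance.

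**Step 4: where the gain comes from.** In the logistic model, adding sex does not reduce the standard error. At a 20-point gap and log odds ratio -1.5, the SE rises from 0.703 to 0.751 while the mean estimate moves from -1.53 to -1.66. The ratio of estimate to SE goes from 1.53/0.703 = 2.18 to 1.66/0.751 = 2.21. The two models estimate different quantities: a marginal and a conditional odds ratio.

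**The case against.** The strongest reply is that nothing in the documents shows sex to be prognostic for this endpoint. Section 1.2 calls it a potential source, lists it beside genetics, personality and substance use, and is discussing the rise in craving from neutral to drug cues. The endpoint in 8.2 is any craving at all after alcohol cues, which is a different quantity. At gaps up to about 20 points the loss is within 2 points of power, and any error is on the safe side. Sections 6.2 and 8.2 label craving the secondary outcome, although the synopsis and 2.1 place it under the primary objectives. The feasibility and acceptability criteria are untouched, and the plan makes no power claim that this would undo. All of this stands, and it is why the point is conditional and modest.

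A reader might infer that the unadjusted standard error is certainly too large, that the test certainly runs below its nominal level, or that the planned comparison is invalid. The documents do not support any of these. The first two need a sex effect that is nowhere quantified, and the first also fails on the log-odds scale, where adjustment raises the SE. The third fails because leaving sex out neither inflates type I error nor biases the marginal comparison when the arms are balanced.

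The reply does not remove the basic mismatch: the randomisation factor is absent from the analysis, and 8.2 leaves its later inclusion open.

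**Conclusion.** The point holds in conditional form. Sex is the only named urn factor and is absent from the craving analysis. If sex is prognostic for any craving, the unadjusted comparison is conservative on the risk-difference scale. The cost at about 21 per arm is about 0 to 2 points of power for gaps up to 20 points, about 3 to 4 at gaps of 25 to 30, and about 6 to 10 at 40, depending on the test. If sex has no effect, nothing is lost by leaving it out and nothing material by including it.

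These sizes rest on assumed craving rates, a treatment log odds ratio of -1.5, equal numbers of each sex and 42 analysed. They also assume one outcome per subject; 8.2 does not say whether the GEE uses more than one rating per person.

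**What to change.** In 8.2, prespecify analysis by the randomisation factor, in one of two ways:

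- a sex-stratified (Mantel-Haenszel) risk difference with the corresponding stratified test; or
- sex as a covariate in the GEE, stating the link and the scale on which the effect is reported, since the conditional odds ratio differs from the marginal one, with the Mantel-Haenszel analysis as the named fallback if the model separates or does not converge.

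In 4.6.1, say that the urn balances the arms on sex.

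Section 8.2 is written in the past tense. If the comparison has already been run, report the planned unadjusted result and label the sex-adjusted one post hoc.

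The cost is one extra model term or stratifier, a sentence or two of text, and occasional non-convergence at this sample size if the covariate model is chosen. The Mantel-Haenszel option avoids the convergence problem, but as the main analysis it would replace the GEE that 8.2 names.

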4.6.2 Blinding

Atomoxetine and placebo capsules will be identically matched in appearance and the blister cards labeled not to reveal the drug identity. The principal investigator or designated study physician will make the decision to unblind the identity of the investigational product if the study blind needs to be broken to

make medical decisions regarding subject treatment. If it is determined that unblinding is necessary to assess AEs or SAEs for expedited reporting, the Data and Safety Monitoring (DSMB) may request unblinding of a subject. The principal investigator will notify the medical monitor.

4.6.3 Interventions on Study Week 1, Day 1 (Baseline Visit)

After the subject is randomized, s/he will receive the first blister pack of study drug. Project staff will explain the dosing plan to the subject.

Every study subject will be provided with a **wallet card** and instructed to carry this card that identifies the potential investigational products that s/he could be taking during the study. The card will provide the name and 24-hour phone number of the investigator (study physician) who can be contacted in the event of an emergency. The card will also instruct the non-study physician rendering emergency care to contact the study physician and inform him/her about the care.

Visits may be scheduled and conducted on any day of the week. Visits can be conducted outside of the scheduled study week, but only based upon subject request (e.g., for reasons related to patient non-compliance with the study schedule) and with prior approval from the principal investigator. Each subject will receive a visit schedule to take home for future reference.

4.6.4 Study Week 1 Telephone Contact

On Study Week 1, Day 3 subjects will be called for a safety assessment including alcohol withdrawal symptoms and given a reminder their dose will increase Study Week 1, Day 4.

4.6.5 Maintenance Phase

During the six-week active treatment phase of the study (Study Weeks 1 to 6), subjects will be seen in person at our offices or remotely, as needed and appropriate, each week. Reminder phone calls, text messages, and/or emails will be sent prior to each visit.

Note that the maintenance phase begins 4 days after study drug administration (Week 1 Day 1). The Week 1 visit needs to be completed between Week 1 Day 3 and Week 1 Day 7 (inclusive).

An alcohol breathalyzer will be administered at each visit, prior to any study assessments, to determine if the subject meets the BrAC requirement of a BrAC ≤ 0.00 before proceeding with assessments. A urine drug test will be performed at each visit. At each of the clinic visits, subjects will meet with one or more study staff members who will assess for possible adverse events since the last visit, take vital signs, inquire about other medication use and assess drinking by TLFB. Pregnancy test and birth control methods (if female) will be assessed.

A new supply of investigational product will be given and the blister cards from the previous period will be collected and a capsule count will be performed for accountability. Blister cards with unused capsules will be returned to the subject. The dosing schedule will be reviewed. The subject will be instructed to bring the blister cards with them to the next visit so the project staff can perform drug accountability (capsule counts). The subject will also be instructed to contact project staff if they are experiencing any intolerable adverse events and/or are contemplating drug discontinuation.

Additional in-clinic visits are permitted under the protocol, if needed, due to the following circumstances: (a) the subject has concerns either about the medication or their drinking and wishes to be seen at a time other than their next scheduled in-clinic visit, (b) the subject has missed a visit and wishes to resume regular participation before their next scheduled visit, (c) the subject has reported some change in health, functioning, or circumstances that necessitates a visit to conduct safety assessments and evaluate the risk

of continued participation in the trial, (d) clinical laboratory measurements need to be repeated, or (e) a study physician or principal investigator deems it necessary.

Subjects desiring additional counseling or professional therapy for non-crisis psychiatric matters (e.g., family or relationship problems, transient school issues) will neither be discouraged from such activity nor asked to postpone until their study participation is concluded. Subjects who initiate outside psychotherapy during the study will not be withdrawn. Subjects may (or may not) be withdrawn if they start new medications, at the discretion of the study physician, if there are any safety concerns.

During the Study Week 5 clinic visit, subjects will complete a second H-LAB paradigm session, which will follow the same procedures as the pretreatment baseline assessment session.

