3.3 Investigational Product Storage and Stability

Kits will be stored at room temperature (within the range of 59°F to 86°F) in a secured area at the clinical site. Our facility, the Brown University Center for Alcohol and Addiction Studies (CAAS), is restricted to authorized personnel, with a security guard stationed 24/7 at the building's entrance. CAAS has a secure alarmed and monitored room for onsite drug storage, dispensing and record keeping. This area is DEA approved for the storage and monitoring of controlled substances. Only authorized personnel have access to the room. Our facilities have adequate lighting, ventilation, temperature, sanitation, humidity, space, and security for suitable storage. Storage areas are secure from unauthorized entry, clean, sanitary, and orderly. Each incoming shipment of medication from the compounding pharmacy is carefully inspected for identity and possible damage of the drug products. All medications are stored at appropriate temperatures and under appropriate conditions in accordance with requirements, if any, in the labeling of such drugs, or with requirements in the current edition of an official compendium, such as the United States Pharmacopeia/National Formulary (USP/NF).

Outdated, damaged, and otherwise unused medication is stored in a separate secure location and container from other medications; the pharmacy disposes of all outdated, damaged, and otherwise unused medication. We develop and maintain study medication logs where we record all transactions regarding the receipt and distribution or other disposition of medications. These records include the source of the medications, and the identity and quantity of the medications received, distributed, and returned to the pharmacy.

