3.4 Investigational Product Dispensing

One blister card containing 7 days of drug/placebo and 1 additional (emergency) blister card containing 7 days of drug/placebo will be distributed after randomization (and on or prior to Study Week 1, Day 1). Each week the subject will receive a new blister card with enough medication for 7 days of drug/placebo. The extra blister card will be collected at the end of the study or at the next clinic visit if drug/placebo was used during the week prior. A second emergency blister card will be dispensed if the subject returns the first used emergency blister card prior to the end of the study.

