3.5 Investigational Product Accountability

The principal investigator, [name] Jr., or designated study personnel will maintain a log of the receipt of all investigational products and record of dispensing of all investigational products to the subject. Investigational product for each subject will be inventoried and accounted for throughout the trial. The principal investigator or his staff will count the capsules remaining at the end of the study and record the capsules count on the appropriate drug accountability form. Subject compliance with investigational product will be assessed by comparing unused capsule count to dispensing logs and dosing records (number of capsules dispensed, number of capsules prescribed, versus the number returned). Subjects will also be asked to account for any missing capsules. If the blister card is not returned, the subject will be asked to report daily drug self-administration.

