3.6 Investigational Product Administration

A licensed individual (i.e., study physician, nurse practitioner) or their designee will ensure the appropriate study medication packets will be dispensed to the appropriate study subject (i.e. perform a drug utilization review on all study medication prior to it being given to a study subject).

One blister card containing 7 days of drug/placebo and 1 additional (emergency) blister card containing 7 days of drug/placebo will be distributed after randomization (and prior to Study Week 1, Day 1). Each week the subject will receive a new blister card with enough medication for 7 days of drug/placebo. The extra blister card will be collected at the end of the study or at the next clinic visit if drug/placebo was used during the week prior. A second emergency blister card will be dispensed if the subject returns the first used emergency blister card prior to the end of the study.

Atomoxetine will be self-administered by subjects once daily after eating and with a full glass of water beginning on Study Week 1, Day 1 and continuing through Study Week 6, Day 7. The first dose will be taken in the study clinic whenever possible. Subjects will be provided with water and a snack to take with first dose. Dose will be titrated, as tolerated, to a target dose of 80 mg once per day of atomoxetine. Dose titration and maintenance will occur as shown in **Table 1**. Capsules should be swallowed whole and should not be cut, crushed, or chewed.

Atomoxetine – Proof-of-Concept Trial

NCT#: NCT04565288

Table 1: Schedule of Administration of Investigational Project

		AM Dose	PM Dose
Study Period	Time Period	(# of capsules)	(# of capsules)
Titration	Study Week 1, Day 1 – 3	40 mg (1)	None
Maintenance	Study Week 1, Day 4 – Week 6, Day 7	40 mg (2)	None

Missed Doses: If a subject misses more than one dose of investigational product, s/he will be instructed to re-start taking the investigational product at the dosage level that s/he was taking before stopping. If one dose of investigational product is missed, s/he should take it immediately unless it is close to the time for the next dose. In that case the subject should skip taking the missed dose of investigational product and wait until the usual time to take their next dose of investigational product. The subject should not double up doses.

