4.6.6 Telephone Assessments

A brief telephone interview (approximately 10 minutes) will occur if a subject misses a clinic visit but agrees to check-in by telephone to assess AEs, concomitant medication use and the emergence of withdrawal symptoms, to encourage the subject to continue taking investigational products, to verify that the subject is taking the prescribed dose, and to remind the subject of the next scheduled visit and dose increases. A summary of the telephone script follows:

- 1. **AEs:** An open-ended question will be asked as follows: "How have you been feeling since your last clinic visit or phone contact?" If the subject reports a new AE, the resolution of an AE, or a change in the severity of an AE, ask additional questions to determine the severity and dates of occurrence or resolution.
- 2. **CIWA-AR:** Subjects will be assessed for the emergence of withdrawal symptoms using the CIWA-AR. The subject may be asked about changes in drinking status after responses to the CIWA-AR interview indicate significant withdrawal.
- 3. **Concomitant Medications:** Ask the following question: "Have you taken any new medications since you were last seen in the clinic or since our last call? If the subject responds affirmatively, record the name of the medication, the daily dose, route of administration, and reason used. If the medication is contraindicated for the study, then notify a study physician, nurse practitioner, or physician assistant for follow-up with the subject.
- 4. **Drug Compliance:** Verification that the subject is taking the prescribed dose and a reminder to take investigational product and to return the blister card(s) with untaken capsules at the next visit will be made. During the Study Week 1 telephone contact, the subject will be reminded of the drug escalation schedule.
- 5. **Reminders:** Remind the subject of their next scheduled clinic visit, and adjust the date within the visit week if they have a conflict.

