4.10 Conducting Sessions Remotely

Study visits may be conducted remotely, when necessary. By limiting in-person contact, allowing remote sessions may effectively decrease COVID-19-related risks. At the study physician's discretion, the physical exam may be conducted via the Brown University HIPAA-compliant Zoom platform (either in an adjacent room or remotely). Research staff still need to collect vital signs, weight, a urine toxicology drug screen, and a urine pregnancy best (if biological sex at birth is female) in person (prior to the physical exam). Blood chemistry and related tests must be done at a local laboratory.

For weekly visits, Zoom video conferencing will be used to conduct the session for those items amenable to remote collection. Extra medication will be mailed from participants to the laboratory via pre-paid postal mail. When remote sessions are held, biospecimen collection will not be done. Even so, to capture biospecimens on a regular basis, no two consecutive post-randomization weekly checkups may be done remotely unless approved beforehand by a study physician.

Dose-Adjustment Criteria

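### Section 4.6.5 sends missed capsules home with a full new weekly card, so surplus drug builds up and section 3.5 needs a rule for counting carried-over capsules

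*Combined protocol and SAP*

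**What the plan says.** Section 4.6.5 describes the weekly visit: "A new supply of investigational product will be given and the blister cards from the previous period will be collected", a capsule count is done, and then "Blister cards with unused capsules will be returned to the subject". The subject brings the cards to the next visit to be counted again.

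Section 3.4, repeated in 3.6, fixes the supply: "Each week the subject will receive a new blister card with enough medication for 7 days of drug/placebo". Nothing reduces it for capsules carried over. One 7-day emergency card is also issued after randomization, and a second only if the first, used, is handed in. Section 3.1 gives the purpose of the extra cards: a lost card or a late appointment. On missed doses, section 3.6 says "The subject should not double up doses".

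For remote visits, section 4.10 says "Extra medication will be mailed from participants to the laboratory via pre-paid postal mail".

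Section 3.5 has staff "count the capsules remaining at the end of the study" and assesses compliance by comparing capsules dispensed and prescribed with those returned. Subjects are asked to account for missing capsules, and self-report is used when a card is not returned.

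**The concern.** A capsule whose scheduled day has passed has no role left in the plan. It may not be doubled up, the coming week has its own card, and loss or lateness is what the emergency card is for. Handing it back adds to the drug held in the homes of adolescents who are drinking. The plan otherwise limits spare drug by allowing one emergency card at a time, and hand-back works around that limit. The subjects who take least accumulate most.

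The second issue is bookkeeping. A capsule that has been counted and handed back must come back again to be reconciled. It can be lost in between, or entered as unused at several visits. Section 4.6.5 has weekly counts and section 3.5 a final count, and neither says how the two are combined.

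**Working it through.** The documents state no adherence rate, capsule total or surplus, so there is no figure of the plan's own to reproduce.

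**Inputs.** Table 1 (section 3.6) gives one capsule a day on Days 1 to 3 and two a day from Day 4 to Week 6 Day 7. Assumptions: a constant share *a* of capsules is taken each week; visits are in clinic at the end of each week; the emergency card holds 14 capsules (7 days at two a day) and is unopened.

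**Supply.** Week 1: 3×1 + 4×2 = 11. Weeks 2 to 6: 14 each. Total: 11 + 5×14 = 81. Through Week 5: 11 + 4×14 = 67.

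**Surplus at home.** Carried-over capsules when the Week 5 card is counted are (1 − *a*) × 67. Stock leaving that visit is 14 (Week 6 card) + 14 (emergency card) + surplus, against 28 if overdue capsules are kept.

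| Assumed share taken | Surplus | Stock with hand-back | Stock if kept | Difference |
|---|---|---|---|---|
| 95% | 3.4 | 31.4 | 28 | +12% |
| 90% | 6.7 | 34.7 | 28 | +24% |
| 80% | 13.4 | 41.4 | 28 | +48% |
| 70% | 20.1 | 48.1 | 28 | +72% |

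Section 1.3 describes one capsule a day throughout, which gives 6×7 = 42 capsules instead of 81. On that reading, 80% taken leaves 0.2 × 35 = 7 carried over, and stock is 7 + 7 + 7 = 21 against 14 (+50%). The pattern does not depend on which count applies, but any capsule count needs the two passages reconciled.

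**What the compliance figure would show.** Take a subject who takes 80% every week. Unused capsules on hand at the end of Weeks 1 to 6 are 2.2, 5.0, 7.8, 10.6, 13.4 and 16.2.
- Cumulative, all cards back: 1 − 16.2/81 = 80%, the true rate.
- Final count alone, handed-back capsules lost, only Week 6's 0.2×14 = 2.8 left: 1 − 2.8/81 = about 97%.
- Weekly counts added as if each were new: the sum is 55.2, and 1 − 55.2/81 = 32%.

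The plan prescribes neither of the last two, and excludes neither.

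**Capsules not yet due.** Section 4.6.5 allows the Week 1 visit from Day 3. A fully adherent subject then still holds 11 − 3 = 8 capsules for Days 4 to 7. If the next visit is Week 2 Day 7, Days 4 to 14 need 11×2 = 22 capsules: the 14 on the new card plus those 8.

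**The case against.** Several stronger readings are tempting, and the documents do not support them.

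*That sections 3.3 and 4.6.6 also contradict hand-back.* Section 3.3 says "the pharmacy disposes of all outdated, damaged, and otherwise unused medication", but it governs stock held at the site and does not say when drug is taken back from subjects. The telephone reminder in section 4.6.6 to "return the blister card(s) with untaken capsules at the next visit" fits a return for counting. Only section 4.10 is in real tension with 4.6.5. Even there, 'extra' may mean the emergency card, since sections 3.1 and 3.4 use the word that way.

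*That hand-back makes the compliance figure unreliable, so that a poor taker can look perfect.* Cards are counted before they go back, so missed capsules are already on record. Dispensing logs, dosing records and questions about missing capsules add further checks. A cumulative reconciliation gives the true rate under hand-back if the cards return. What stands is narrower: section 3.5 itself provides for cards that do not return, and the method of combining counts is unstated.

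*That every leftover capsule should be kept.* At a Week 1 Day 3 visit, keeping all capsules and logging them as not taken would record a fully adherent subject as missing 8 of 11 (73%). It could also leave that subject 8 capsules, or 4 days, short unless the emergency card were opened. Hand-back has a legitimate purpose for capsules not yet due.

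*That the craving result is compromised.* Adherence is not an endpoint, has no threshold and enters no stated analysis. Section 4.7 separately asks, where possible, for self-reported or observed dosing on the day of the laboratory session.

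It is also fair to say that the emergency card puts spare capsules at home by design, that section 4.3.2 excludes past suicide attempts and current suicidality risk, and that at high adherence the surplus is small.

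**Conclusion.** The point holds in a limited form. As written, section 4.6.5 sends overdue capsules home with a full new card and no offset, and they serve no further purpose there. The surplus by the Week 5 count runs from about 3.4 capsules at 95% taken to 20.1 at 70%. These figures rest on assumed adherence rates, Table 1 counts and end-of-week clinic visits. The count in section 3.5 can be done correctly under hand-back, but the plan does not say how carried-over capsules are logged and so leaves room for loss or double counting. The different treatment of clinic and remote visits needs to be reconciled or explained.

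This is a cheap, minor improvement. It changes no primary endpoint and no craving analysis.

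**What to change.** - **Section 4.6.5.** After the count, keep at the site the capsules whose scheduled day has passed and handle them under section 3.3. A card still holding capsules not yet due (for example at a Week 1 Day 3 visit) goes home, is logged as carried over and is collected at the next visit. The sponsor should first confirm whether the present sentence is a slip, with 'to' written for 'by' the subject. If so it still needs correcting, because staff will follow it as written.
- **Section 4.10.** Reconcile mail-back with the same rule and say what 'extra' covers.
- **Section 3.5.** Compute compliance cumulatively from capsules dispensed and prescribed, with each capsule counted once.
- **Table 1 and section 1.3.** Reconcile the number of capsules per day (81 against 42 over six weeks), since every count depends on it.

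The cost is a few sentences and slightly more logging at visits. No visits are added, and the storage and disposal routes already exist in section 3.3.
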